**10.4 PK Parameters Calculated With Urine Concentrations**

In study Part 1, urine will be collected for quantitation for PK analysis. Urine samples will be collected at 6 times or time intervals: spot pre-dose (within 2 hours before dosing), 0-4 hours, 4-8 hours, 8-12 hours, 12-24 hours, and 24-32 hours post-dose.

Urine samples will be used to calculate the following parameters for resveratrol, resveratrol-3-glucuronide, resveratrol-4'-glucuronide, and resveratrol-3-sulfate:

Ae 0-t :	Cumulative urinary excretion from time zero to time t, calculated as the sum of the amounts excreted over each collection interval. The amount excreted in urine for each time interval is calculated as the urine concentration multiplied by the urine volume.
---------------------	--

---

$R_{\max}$ :	Maximum rate of urinary excretion, calculated by dividing the amount of drug excreted in each collection interval by the time over which it was collected.
$T_{\max}$ :	Time of $R_{\max}$ , calculated as the midpoint of the collection interval during which $R_{\max}$ occurred.
$CL_r$ :	Renal clearance, calculated as $Ae_{0-t}/AUC_{0-t}$ (plasma) where t is $T_{\text{last}}$

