## 10. Pharmacokinetic Analyses

### 10.1 Handling of the Below the Lower Limit of Quantification (BLQ) and the No Reportable Concentration

All concentration values that are BLQ occurring prior to dosing as well as samples with no reportable value (NRV) occurring prior to dosing will be replaced by "0.00"; otherwise they (BLQ and NRV) will be set to missing for tabulation, graphical representation and calculation purposes.

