### 10.3 Pharmacokinetic Parameters

PK analyses will be performed using Phoenix® WinNonlin® version 8.2, which is validated by Syneos Health. Inferential statistical analyses will be performed using Statistical Analysis System (SAS®) version 9.4 according to FDA guidelines. Bioanalysis of all samples should be completed prior to the initiation of the PK statistical analyses.

A total of 17 blood samples will be collected in each period for PK analyses: pre-dose and 0.133, 0.250, 0.500, 1.00, 1.50, 2.00, 3.00, 4.00, 5.00, 6.00, 8.00, 10.0, 12.0, 16.0, 24.0, and 32.0 hours post- dose.

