#### Primary parameter:

AUC0-inf: Area under the concentration-time curve from time zero to infinity (extrapolated), calculated as  $AUC_{0-t} + C_t/K_{el}$ , where  $C_t$  is the last observed measurable concentration.

---

AUC 0-t :	Area under the concentration-time curve from time zero to the last measurable concentration. AUC 0-t will be calculated using the linear trapezoidal-linear interpolation method.
C max :	Maximum observed concentration.

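### Renal clearance is defined at plasma Tlast, but urinary excretion is known only at urine-interval ends, so the two windows cannot match when Tlast falls inside an interval

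*SAP*

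**What the plan says.** SAP 10.4 lists four urine parameters. The last is "Renal clearance, calculated as" Ae0-t over plasma AUC0-t, with t equal to Tlast.

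- **Numerator.** In the same section Ae0-t is "calculated as the sum of the amounts excreted over each collection interval". The post-dose intervals are "0-4 hours, 4-8 hours, 8-12 hours, 12-24 hours, and 24-32 hours post-dose".
- **Denominator.** SAP 10.3 defines AUC0-t as "Area under the concentration-time curve from time zero to the last measurable concentration". Under SAP 10.1, for post-dose samples below the quantification limit, "otherwise they (BLQ and NRV) will be set to missing", so the AUC stops at Tlast.
- **Plasma times.** SAP 10.3 lists 16 post-dose samples, the later ones at "3.00, 4.00, 5.00, 6.00, 8.00, 10.0, 12.0, 16.0, 24.0, and 32.0 hours".
- **Bridging.** SAP section 12 rules out interpolation or extrapolation for missing PK data.
- **Use.** SAP 10.5.5 plans summary statistics only for urine. CLr is absent from protocol 12.1.2 and SAP section 5, although SAP section 4 reports no change in planned analyses.

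**The concern.** Renal clearance is a ratio of amount excreted to exposure over one and the same time window. The formula uses a single t in both terms, so matched windows are plainly intended. But the plasma t can be any of 16 sampling times, and the urine t only one of five. For the other 11 plasma times, Ae0-Tlast cannot be calculated as defined. The analyst must choose which whole intervals to put above the AUC, and each choice covers a window that is too short or too long.

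Two analysts following the SAP could therefore report CLr values from the same data with errors of opposite sign. Because Tlast is specific to subject, period and analyte, and tends to lengthen with dose, the error could also differ between 200, 500 and 1000 mg and be mistaken for a change in renal handling.

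**Working it through.** The documents state no CLr for JOTROL, so there is no plan figure to reproduce. As a check that protocol Table 1 was read correctly: 500 mg / 223.7 ng·h/mL = 2,235 L/h, the CL/F listed there.

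**Inputs**
- Urine-interval ends: 4, 8, 12, 24, 32 h (SAP 10.4).
- Plasma times that are not urine-interval ends: 0.133, 0.25, 0.5, 1, 1.5, 2, 3, 5, 6, 10, 16 h (SAP 10.3).
- Half-lives 2.85, 4.22 and 8.87 h; Tmax 0.833 h; Cmax 72.6 ng/mL at 500 mg (protocol Table 1, unmodified resveratrol; the 2.85 h value comes from one participant).
- Assumptions: one-compartment oral profile, Cmax proportional to dose, plasma quantification limit (LLOQ) between 0.1 and 5 ng/mL.

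**Formula.** With constant true renal clearance, Ae(0-U) = CLr × AUC(0-U). If urine to time U is divided by AUC to Tlast, relative bias = AUC(0-U)/AUC(0-Tlast) − 1. In the model, AUC(0-U) is proportional to (1 − e^(−kU))/k − (1 − e^(−aU))/a, where k = ln 2/half-life and a is the absorption rate that puts Tmax at 0.833 h.

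**Example.** Half-life 2.85 h gives k = 0.2432 and a = 3.415 per hour. The AUC terms are 3.231 (8 h), 3.458 (10 h), 3.597 (12 h) and 3.817 (32 h). At Tlast 10 h:
- completed intervals only: 3.231/3.458 − 1 = −6.5%
- through the interval containing Tlast: 3.597/3.458 − 1 = +4.0%
- all urine to 32 h: 3.817/3.458 − 1 = +10.4%

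**Bias over half-lives 2.85 to 8.87 h**

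| Tlast | Completed intervals only | Through interval containing Tlast | All urine to 32 h |
|---|---|---|---|
| 5 h | −13% to −18% | +24% to +46% | +47% to +193% |
| 6 h | −21% to −30% | +13% to +25% | +33% to +152% |
| 10 h | −7% to −15% | +4% to +13% | +10% to +71% |
| 16 h | −4% to −15% | +2% to +19% | +2% to +29% |
| 4, 8, 12, 24 or 32 h | 0 | 0 | not 0 unless Tlast is 32 h |

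**Dose, all urine to 32 h, 200 mg versus 1000 mg**

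| Assumed LLOQ | Half-life 2.85 h | 4.22 h | 8.87 h |
|---|---|---|---|
| 5 ng/mL | +18% vs +6% | +25% vs +8% | +29% vs 0% |
| 1 ng/mL | +6% vs +2% | +8% vs +2% | 0% vs 0% |
| 0.1 ng/mL | at most 0.3% at every dose | same | same |

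Under the other two conventions the bias need not fall with dose. With half-life 2.85 h and LLOQ 1 ng/mL it is 0 at 200 mg (Tlast 12 h), but −4% or +2% at 500 and 1000 mg (Tlast 16 h).

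**How early can Tlast be?** Modelled Cmax at 200 mg is 72.6 × 200/500 = 29.0 ng/mL. For Tlast to be 10 h, the 10 h sample must be measurable and the 12 h sample not. That needs an LLOQ of about 2.1 to 3.4 ng/mL with half-life 2.85 h, but about 12.3 to 14.4 ng/mL with 8.87 h.

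**The case against.** The strongest reply has four parts.

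1. *The formula already says one t for both terms.* This stands as to intent, and where Tlast is an interval end and Ae is cut there, the bias is zero. It does not supply a numerator for the other Tlast values.
2. *Using all urine to 32 h would depart from t = Tlast.* This is fair. A reader might infer that this is the likely outcome and that it produces a false dose trend. Nothing in the documents shows that urine stays measurable longer than plasma or that this convention would be chosen.
3. *The large figures pair a long half-life with an early Tlast.* This also stands. The LLOQ needed for the +71% case is over 40% of modelled Cmax (12.3/29.0 = 42%). Table 1 also suggests faster effective decline: ln 2 × AUC/Cmax at 1 g is 0.693 × 544.8/117.0 = 3.2 h, and the other doses give 1.7 to 2.1 h (approximate; the 0.5 g AUC is from one participant). At 3.2 h with simple exponential decline, the 10 h factor with urine to 32 h is (1 − e^(−0.2166×32))/(1 − e^(−0.2166×10)) = 1.13.
4. *Little depends on CLr.* This is true. It enters neither the dose-proportionality nor the food-effect analysis, and Table 1 shows CVs of 53% to 139% for it. Metabolite concentrations in Table 1 are far above the parent's, so their Tlast is plausibly late.

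What is left is a definition that cannot be applied to some profiles.

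**Conclusion.** The point holds conditionally. For any profile whose Tlast lies inside a urine interval, the stated rule cannot give matched windows, and any choice of whole intervals biases CLr. At Tlast 10 h the bias is about −7% to −15%, +4% to +13% or +10% to +71%, according to the convention. The upper end of the last range is a bound rather than an expectation.

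The documents do not support saying that CLr is biased in every profile, or that the bias necessarily changes with dose. Its sign depends on an unstated convention. Its size and dose pattern depend on the LLOQ and JOTROL's Tlast, neither of which is given, and on borrowing the kinetics of unmodified resveratrol. With an LLOQ of 0.1 ng/mL it is negligible at all doses. Parent resveratrol at 200 mg is most exposed. The consequence is confined to one descriptive parameter, but the remedy costs almost nothing and should be adopted.

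**What to change.** Replace the CLr line in SAP 10.4 with CLr = Ae0-T*/AUC0-T*. T* is the last urine-interval end (4, 8, 12, 24 or 32 h), by scheduled time, at or before the scheduled time of the last measurable plasma concentration. Report T* for each profile, and do not report CLr when scheduled Tlast is before 4 h.

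Scheduled times are needed for choosing T*. SAP 10.2 works with actual times, and protocol 9.7.1 allows late samples to be drawn up to 3 minutes early. A nominal 24 h sample taken at 23.97 h would otherwise push T* back to 12 h.

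Every urine-interval end is also a plasma sampling time, so the partial AUC needs no interpolation between scheduled samples. In the model above the mismatch bias falls to 0%, leaving linear-trapezoid error of about −1.2% to +0.6%. Protocol Table 1 follows the same principle, with 24 h urine over AUC0-24.

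The cost is two SAP sentences, one partial AUC per profile, and some late urine not used for CLr. In the same edit, add CLr to SAP section 5 and record it in section 4 as an addition to the protocol's urine parameters.

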## 10.5 Statistical Analyses

### 10.5.1 PK Parameters in Plasma

Individual and mean plasma concentration versus time curves will be presented for both linear and semi-log scales. Descriptive statistics (number of observations, arithmetic and geometric means, SD, coefficients of variation [CV%], Min, Max, and median) of the plasma concentrations versus time data will be presented by Treatment as well for the PK parameters. Summary statistics will be used to describe the PK profile for each treatment.

### 10.5.2 Assessment of Dose Proportionality

Dose proportionality analysis for  $AUC_{0-t}$ ,  $AUC_{0-\text{inf}}$  and  $C_{\max}$  will be performed (using the power model with mixed procedure from SAS®) considering data under fasting conditions (Periods 1, 2, and 3).

Power model will include the PK parameter as the response variable and dose (mg) as the explanatory variable. For this model, the variable dose will be treated as a continuous variable.

The form of the model is as follows:

PK Parameter =  $a \times \text{Dose}^b \times e^{\epsilon}$ , where  $\text{Dose} \geq 0$ , and  $e^{\epsilon}$  represents the associated error.

Thus, perfect dose proportionality is met when  $b=1$  (ignoring error). This becomes a linear relationship following a natural-log transformation, The mixed effect statistical model will be the following:

$$\ln(P_{ij}) = \ln(a) + b \cdot \ln(\text{Dose}_{ij}) + s_i + \epsilon_{ij},$$

where  $P_{ij}$  is the value in the  $j^{\text{th}}$  period for the  $i^{\text{th}}$  subject for the PK parameter analyzed,  $\text{Dose}_{ij}$  is the dose in the  $j^{\text{th}}$  period for the  $i^{\text{th}}$  subject,  $s_i$  is the random effect associated to the  $i^{\text{th}}$  subject, and  $\epsilon_{ij}$  is the random error in the  $j^{\text{th}}$  period for the  $i^{\text{th}}$  subject. The  $s_i$  and  $\epsilon_{ij}$  values are assumed to be mutually independent and normally distributed.

The estimate of b together with a 90% confidence interval (CI) will be provided (for each PK parameter model), and this will be used to quantify dose proportionality.

---

```

proc mixed data=dataset;
class subject;
model ln_pk_parameter = ln_dose / solution;
random subject;
estimate 'Beta Estimate' ln_dose 1 / cl alpha=0.1;
ods output estimates = estimates;

run;
```

The PK parameter values estimated from the power model will be plotted against dose. This plot will also include individual subject values  $\pm$  SD (separately by dose level).

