### 3.5 Sample Size

A total of 24 healthy adult male or female volunteers will be included in study Part 1. Only 16 subjects who completed study Part 1 will be included in study Part 2. These 16 subjects will be selected according to their order of enrolment in the study, provided their consent to continue the study, they follow the study restrictions and they still meet study criteria. Subjects numbers are judged adequate to achieve the study objectives.

An effort will be made to include to the extent possible, subjects of the following age groups:

- $\geq 65$  and  $\leq 70$  years of age;
- $\geq 70$  and  $\leq 75$  years of age.

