### 3.6 Randomization and Blinding

Subjects will be administered 200 mg, 500 mg and 1000 mg gelcaps sequentially in ascending order. As this is an open-label study no blinding will be applied.

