### 10.5.3 Criteria for Determination of Dose-Proportionality

PK dose proportionality will be concluded if the 90% C.I. of  $b$  for  $AUC_{0-inf}$ ,  $AUC_{0-t}$  and  $C_{max}$  are entirely contained within the following bounds that depend on the dose range ratio ([Smith BP, 2000](#)) (i.e.,  $\ln(1000/200) = \ln(5)$ ):

- Lower bound =  $1 + \ln(0.80) / \ln(5) = 0.861353116$  and
- Upper bound =  $1 + \ln(1.25) / \ln(5) = 1.138646884$

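### Dose proportionality is concluded from a single slope that the 500 mg dose barely influences, and the rule contains no lack-of-fit check

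*SAP*

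**What the plan says.** SAP 10.5.2 specifies a power model for AUC0-t, AUC0-inf and Cmax over the three fasting periods. Dose enters as a number, not a factor: "the variable dose will be treated as a continuous variable". The fixed part is "model ln_pk_parameter = ln_dose / solution" and the random part is "random subject", a subject intercept. The subject effects and residuals "values are assumed to be mutually independent and normally distributed". The decision quantity comes from "estimate 'Beta Estimate' ln_dose 1 / cl alpha=0.1".

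SAP 10.5.3 turns this into a rule: "PK dose proportionality will be concluded if the 90% C.I. of" b for the three parameters lies inside bounds set by the fivefold dose range, 0.861353116 to 1.138646884.

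On design, SAP 3.6 states "Subjects will be administered 200 mg, 500 mg and 1000 mg gelcaps sequentially in ascending order", and SAP 3.5 states "A total of 24 healthy adult male or female volunteers will be included in study Part 1". Neither document gives a within-subject SD, a between-subject slope SD or a power calculation for this analysis.

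SAP 10.5.2 also plans a plot of model-estimated values against dose together with individual values, and SAP 10.5.1 plans descriptive statistics by treatment. Neither is part of the 10.5.3 rule.

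**The concern.** A power-model slope answers the proportionality question only if one slope describes the whole dose range. With three doses that assumption leaves one degree of freedom for checking it, and the plan does not use that degree of freedom. An average slope near 1 can arise because both dose steps are proportional. It can also arise because exposure per mg goes up in the first step and down in the second. The rule cannot tell the two apart.

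The second issue is the random part. Every subject is meant to receive all three doses, so subjects can differ in slope. The model has no term for this and treats such differences as independent residual error. If they exist, the standard error of b is too small.

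At stake is a statement of dose proportionality over 200-1000 mg when neither dose step is proportional.

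**Working it through.** **Inputs.** From the SAP: doses 200, 500 and 1000 mg, 24 subjects, 90% CI, and the 10.5.3 bounds. Assumed, because the documents give no figure: within-subject CV of 20-50% and slope SD (tau) of 0 to 0.3. Data are taken as complete at the nominal doses, one PK parameter at a time. Simulations used 20,000 or more trials per setting.

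**1. The SAP's own bounds.** ln(0.80) = -0.2231 and ln(5) = 1.6094, so 1 - 0.2231/1.6094 = 0.8614. By symmetry the upper bound is 1.1386. The stated figures reproduce.

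**2. How much each dose contributes to b.** Centred ln doses are -0.842, 0.074 and 0.768. Their sum of squares is Sxx = 1.3034. The weights x/Sxx are -0.646, 0.057 and 0.589, so b is close to a comparison of 1000 mg with 200 mg alone.

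**3. A rise-then-fall example.** Let exposure per mg be 1.29 times the 200 mg value at 500 mg, and 1.29 x 0.77 = 0.993 times it at 1000 mg. Then

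b = 1 + 0.057 x ln(1.29) + 0.589 x ln(0.993) = 1 + 0.0145 - 0.004 = 1.011.

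The misfit goes into the residual and widens the CI, but not by enough to fail the rule at low variability. The simulated chance that the rule concludes proportionality is:

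| Within-subject CV (assumed) | SD on ln scale, sqrt(ln(1+CV²)) | Rule concludes proportionality |
|---|---|---|
| 20% | 0.198 | 91% |
| 30% | 0.294 | 54% |
| 40% | 0.385 | 18% |
| 50% | 0.472 | 2% |

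A within-subject curvature contrast on the same data, tested at 5%, detects this shape in about 99.8% of trials at CV 20% and 91% at CV 30%. With a 50% excess per mg at 500 mg alone, b is 1 + 0.057 x ln(1.5) = 1.023. The rule then still passes in 71% of trials at residual SD 0.2 and 32% at 0.3.

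**4. CI of b if slopes vary between subjects.** With residual SD s, the planned model has 47 residual df. Its expected squared SE is (s² + (23/47) tau² Sxx)/(24 Sxx). The true variance is (s² + tau² Sxx)/(24 Sxx). For s = tau = 0.2, tau² Sxx = 0.0521, and the ratio of SEs is sqrt((0.0400 + 0.0255)/(0.0400 + 0.0521)) = 0.84. Simulated coverage of the nominal 90% CI:

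| s | tau = 0 | tau = 0.1 | tau = 0.2 | tau = 0.3 |
|---|---|---|---|---|
| 0.2 | 90% | 87.7% | 83.3% | 81.0% |
| 0.3 | 90% | 88.9% | 86.4% | 83.4% |

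When b sits exactly on the upper bound, the chance of wrongly concluding proportionality (nominal 5%) is 8.0% at s = 0.2, tau = 0.2; 9.3% at s = 0.2, tau = 0.3; and 6.3% at s = 0.3, tau = 0.2. It is below 5% at s = 0.4.

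**5. The two issues need separate remedies.** Taking the mean of subject slopes (t on 23 df) restores 90% coverage when there is no curvature. Used alone under curvature it makes matters worse, because the misfit no longer widens the CI. With a 50% excess at 500 mg and CV 30%, the chance of concluding proportionality rises from 34% to 60%.

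**The case against.** Several counter-arguments carry weight.

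- **Status and displays.** The protocol (12.3) calls all inference exploratory and allows additional analyses. The planned plot and the geometric means by treatment would let a careful reader see a mid-dose excess. This stands and limits severity. It does not remove the point, because 10.5.3 states a fixed conclusion that ignores those displays.
- **The example is chosen to cancel.** It is: 1.29 x 0.77 is almost exactly 1. A steady slope of 1.28 over the whole range would fail the rule, as it should. The gap concerns opposite deviations only.
- **Variability and joint criteria.** At CV 40% or more the rule rarely passes anything, and it names three parameters together. Both reduce the percentages above, which are for one parameter.

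Two stronger readings are tempting and are not supported. A reader might infer that the planned 90% CI is simply too narrow. That holds only if subjects' slopes differ, for which the documents give no figure. With equal slopes coverage is 90%, and missing curvature widens the CI: at residual SD 0.3 the half-width grows from 0.090 to 0.114 with a 50% excess at 500 mg.

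A reader might also take Protocol Table 1 as evidence of rise-then-fall, since AUCinf per g there is 447, 545, 315 and 264 at 0.5, 1, 2.5 and 5 g. The values above 1 g lie outside this study's range, the 0.5 g value is from one participant, and the product is not JOTROL. Protocol 4.3.2 reports more than proportional exposure at 25-150 mg, also outside the range. These data do not establish curvature over 200-1000 mg.

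**Conclusion.** The point holds as a gap in the decision rule. As written, SAP 10.5.3 can declare proportionality when exposure per mg rises by about 29% at 500 mg and falls back at 1000 mg. The chance is about 91% at CV 20%, 54% at CV 30% and 18% at CV 40%. The trial already collects the data that would reveal this at the lower CVs.

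The slope-variation point is secondary and conditional. Coverage is about 80-89% if the slope SD is 0.1-0.3 and the CV 20-30%, and 90% if slopes are equal.

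All figures rest on assumed variability, 24 complete subjects and the nominal doses. Changed doses would alter the weights and the bounds. Because the analysis is exploratory, severity is low to moderate. This is an inexpensive improvement and does not invalidate the plan.

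**What to change.** **SAP 10.5.2.** Add a mixed model with dose as a class variable on dose-normalised ln AUC0-t, AUC0-inf and Cmax. Report the 500/200 and 1000/500 geometric mean ratios with 90% CIs and a 1-df lack-of-fit (curvature) test. A within-subject contrast with t on n-1 df is a convenient form.

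**SAP 10.5.3.** Conclude proportionality over the range only if the CI of b is within the bounds and the lack-of-fit test is not significant at 5%. Otherwise report the adjacent-dose ratios and make no proportionality claim. In the example above, wrong conclusions then cannot exceed the test's miss rate: about 100 - 99.8 = 0.2% at CV 20% and 100 - 91 = 9% at CV 30%.

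**Sensitivity analysis.** Report the CI of b with a random slope on centred ln dose and an unstructured covariance, or from the mean of subject slopes with t on n-1 df. It should never replace the lack-of-fit check. Centring matters: a random slope on uncentred ln dose with the default covariance gave coverage of only about 80-82% at slope SD 0.3 and CV 20%, and the slope variance collapsed to about zero in a third or more of trials.

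**Cost.** One extra table and a few SAS statements. When proportionality is true, the 5% test takes away about one in twenty correct conclusions (97% to about 93% at CV 20%). The sensitivity CI is wider, for example a half-width of 0.114 against 0.101 at residual SD 0.3 and slope SD 0.2.

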### 10.5.3 Criteria for Determination of Dose-Proportionality

PK dose proportionality will be concluded if the 90% C.I. of  $b$  for  $AUC_{0-inf}$ ,  $AUC_{0-t}$  and  $C_{max}$  are entirely contained within the following bounds that depend on the dose range ratio ([Smith BP, 2000](#)) (i.e.,  $\ln(1000/200) = \ln(5)$ ):

- Lower bound =  $1 + \ln(0.80) / \ln(5) = 0.861353116$  and
- Upper bound =  $1 + \ln(1.25) / \ln(5) = 1.138646884$

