## **2. Study Objectives**

- To characterize the PK profile of JOTROL (resveratrol) following oral administration of SAD ranging from 200 mg up to a dose currently estimated at 1000 mg, in healthy adult subjects.
- To evaluate the effect of food on the PK profile of JOTROL.

---

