### 3. Study Design

#### 3.1 General Design

This will be a single center, Phase 1, open-label, sequential SAD study, with a food-effect arm. The study will be divided into two parts:

- Study Part 1 consists of 3 periods with SAD of JOTROL under fasting conditions. Periods 2 and 3 will be initiated with updated doses after safety, tolerability, and PK data are evaluated by the Safety Committee and deemed acceptable for single doses for subsequent doses.
- Study Part 2 consists of a single oral JOTROL dose under fed conditions. JOTROL dose for this study part will derive from study Part 1 safety, tolerability, and PK data.

In order to minimize potential variability, elder subjects will not be included in the food effect part (Part 2).

This study is intended for submission under FDA regulations.

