## 7. Interim Analyses

Interim PK analyses will be performed between each dose level and will inform selection of the subsequent dose. The Interim Analyses using PK concentration data will be done after the bioanalytical phase is completed and will include data from subjects who have finalized their study visits at the time of the interim database availability.

PK parameters will be calculated using scheduled sampling times as actual sampling times will not be available for these interim analyses. Only descriptive statistics will be calculated and provided. Interim descriptive analyses of the PK variables will be conducted for each period (Number of observations [N], arithmetic mean, standard deviation [SD], coefficient of variation [%CV], median, minimum [Min], maximum [Max], geometric mean, and %CV geom.mean).

---

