### 10.5.4 Food-Effect assessment

For evaluation of the food-effect, PK data (ln-transformed  $AUC_{0-t}$ ,  $AUC_{0-inf}$ ,  $C_{max}$  and untransformed  $T_{max}$ ) reported under fed conditions (Period 4) and under fasting conditions (for the same dose level) will be compared using ANOVA from SAS®. The ratio (fed/fasting) and 90% geometric confidence interval will also be calculated for  $AUC_{0-t}$ ,  $AUC_{0-inf}$  and  $C_{max}$ .

If 90% CI for  $AUC_{0-t}$ ,  $AUC_{0-inf}$  and  $C_{max}$  are within 80.00% to 125.00% then no food effect will be concluded.

For all analytes, using GLM procedure in SAS, ANOVA will be performed on ln-transformed  $AUC_{0-t}$ ,  $AUC_{0-inf}$  and  $C_{max}$  at the alpha level of 0.05. The model will include Treatment as fixed effect and Subject as a random effect. Inter- and intra-subject coefficient of variation will be estimated. The ratio of geometric means and 90% confidence interval for the ratio of geometric means, based on least-squares means from the ANOVA of the ln-transformed data, will be calculated for  $AUC_{0-t}$ ,  $AUC_{0-inf}$ , and  $C_{max}$ .

```

SAS® codes for ANOVA: fed vs. fasting
PROC GLM data=basepk;
CLASS TREATMENT SUBJECT;
MODEL VAR = TREATMENT SUBJECT;
RANDOM SUBJECT;
LSMEANS TREATMENT / cl pdiff alpha=0.1;
ESTIMATE 'fed - fasting' TRT 1 -1/cl alpha=0.1;

run;
```

---

Additional statistical analysis may be performed.

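### Do the provisional doses leave the dose-proportionality limits and the food-effect comparison without a usable rule?

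*SAP*

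**What the plan says.** **Dose proportionality.** SAP 10.5.3 requires the 90% CI of the power-model slope b to be "entirely contained within the following bounds that depend on the dose range ratio". It identifies the ratio as 1000/200 and prints the lower limit as 1 + "\ln(0.80) / \ln(5) = 0.861353116", with the matching upper limit 1.138646884.

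**Doses.** SAP section 2 describes the range as 200 mg "up to a dose currently estimated at 1000 mg". SAP 3.1 says "Periods 2 and 3 will be initiated with updated doses", and SAP section 7 adds: "Interim PK analyses will be performed between each dose level and will inform selection of the subsequent dose". SAP 3.3 and 3.6 nevertheless list 200, 500 and 1000 mg.

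**Food effect.** SAP 10.5.4 says that Period 4 data and data "under fasting conditions (for the same dose level) will be compared using ANOVA". If the 90% CIs "are within 80.00% to 125.00% then no food effect will be concluded". The section closes with "Additional statistical analysis may be performed".

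**Period 4 dose.** Protocol 7.4, 9.3 and 9.5 and the synopsis plan the same dose in Periods 3 and 4. They allow a lower Period 4 dose to keep AUC under the ceiling, and do not require that dose to have been given fasted.

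**The concern.** The plan treats the doses as provisional, but both decision rules are written around the nominal scheme.

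If the top fasted dose changed and someone applied 0.8614 to 1.1386 unaltered, the rule would no longer express the 0.80-1.25 criterion it is built from. It would be too strict below a ratio of 5 and too lenient above it.

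If Period 4 used a dose with no fasted counterpart, the fed/fasting ratio, its 90% CI and the ANOVA would have no comparator. Food effect is one of only two study objectives, and the protocol itself foresees the reduction. With 100 mg gelcaps and fasted doses of 200, 500 and 1000 mg, 7 of the 9 lower whole-gelcap doses (100 to 900 mg) have no fasted match. That is a count, not a probability. A method chosen at that point would be chosen with the fasted results already known, in an open-label study.

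**Working it through.** All doses other than 200, 500 and 1000 mg below are arithmetic examples only.

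**1. The plan's own figure.** Limits = 1 ± ln(1.25)/ln(r), where r is the highest divided by the lowest fasted dose. At r = 5: 0.223144/1.609438 = 0.138647, giving 0.861353 and 1.138647. This matches SAP 10.5.3. The Period 2 dose does not enter.

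**2. Other ratios.** If the printed limits were kept, the criterion they imply for the ratio of dose-normalised means is r^(−0.138647) to r^(0.138647).

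| r | Recomputed limits | Criterion implied by printed limits |
|---|---|---|
| 2.5 | 0.7565-1.2435 | 0.881-1.136 |
| 4 | 0.8390-1.1610 | 0.825-1.212 |
| 5 | 0.8614-1.1386 | 0.800-1.250 |
| 6 | 0.8755-1.1245 | 0.780-1.282 |

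**3. Cost of the misreading.** Take 24 subjects at 200, 500 and 800 mg, true b = 1, one parameter, and an assumed within-subject CV of 25% (the documents give none).
- σ = √ln(1.0625) = 0.2462. The sum of squares of ln(dose) is 0.994, so SE(b) = 0.2462/√(24 × 0.994) = 0.0504.
- With 47 df, the CI half-width is 1.678 × 0.0504 = 0.0846.
- Printed limits: (0.1386 − 0.0846)/0.0504 = 1.07, a chance of about 72%. Recomputed limits: (0.1610 − 0.0846)/0.0504 = 1.52, about 87%.
- Simulation with the error variance estimated gives 71% and 87%. Over assumed CVs of 20% to 50% the figures run from 92% v 98% to 0.5% v 5%.

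This loss occurs only if an analyst ignores the formula printed beside the number.

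**4. What remains if Period 4 has no fasted match.**
- SAP 10.5.1 and protocol 12.3 still give summary statistics of concentrations and PK parameters for every treatment, the fed one included. These need no dose match.
- SAP 10.5.4 does not tell anyone to compare unequal doses. Its wording withholds the 80.00-125.00% conclusion; it does not produce a wrong one.
- SAP section 1 requires added analyses and their justification to be set out in an amendment and in the study report, with prior sponsor approval. The Period 4 dose has to be fixed before any fed sample exists, so an amendment can precede the fed half of the comparison.

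**5. Would naming a model now help?** The natural candidate is the SAP 10.5.2 power model with a fed term, fitted to Periods 1-4 of the 16 Part 2 subjects.
- *Precision.* Let S = 1.303 be the sum of squares of ln(dose) at 200, 500 and 1000 mg, and d the distance of ln(Period 4 dose) from their mean, 6.140. The SE relative to the planned paired contrast is √(2/3 + d²/(2S)): 0.82 at 400 mg, 0.91 at 900 mg, 1.25 at 100 mg.
- *Bias.* Suppose there is no food effect and the true log-log slope is 1 up to 500 mg and 2 from 500 to 1000 mg. On the log scale the fasted values are 0, 0.916 and 2.303, and the fitted slope is 1.408. At 400 mg the truth is 0.693 and the line gives 0.864, so the fed/fasting ratio reads exp(−0.170) = 0.84. At 900 mg it reads 1.09. At 100 mg the truth is −0.693 and the line gives −1.089, so it reads 1.49. With an upper slope of 1.5 these become 0.92, 1.04 and 1.22.

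The model is therefore least reliable when exposure rises faster than dose, which is the situation that would prompt a reduced Period 4 dose.

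**The case for a change.** The strongest opposing case concerns food effect. The permission for further analyses in SAP 10.5.4 and the amendment route in SAP section 1 allow a comparison without fixing one. One sentence would settle it at almost no cost, and SAP 10.5.4 does state a formal conclusion even though protocol 12.3 calls all inference exploratory. It stands that the contingency is unwritten, and that SAP section 1 permits but does not oblige the amendment to come before fed data.

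It does not carry further. Only the ratio, its CI and the ANOVA are lost; the summaries are not. Knowing the fasted data alone gives little room to steer a fed/fasting ratio. The candidate model would itself have to be reported descriptively, so what it adds to the planned summaries is small.

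On proportionality, the fair residue is editorial: r is not defined in words as a ratio of doses actually given. Protocol 7.3 allows the Period 2 and 3 doses to be increased, while the synopsis and 9.5 say they will not exceed those outlined. Those passages contradict each other and must be reconciled. That is a separate matter, since the limits formula works in either direction.

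**Conclusion.** No change follows. The proportionality limits are correct for the planned doses, and the text already says they move with the dose ratio. Recomputing them is the natural reading, and b with its 90% CI is reported whatever the limits. The loss of about 16 points in the example (87% to 71% at r = 4 and CV 25%) measures a misreading, not the plan.

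The food-effect gap is a conditional contingency that analysts would fill sensibly: summarise fed and fasted exposure, draw no 80.00-125.00% conclusion, and specify any dose-adjusted ratio by amendment. It arises only if Period 3 exposure is higher than expected, the Period 4 dose is then reduced, and the reduced dose was given in no fasted period. The documents give no basis for a probability. If Period 4 repeats any fasted dose, the planned comparison can be run as written.

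This rests on the comparison being exploratory, as protocol 12.3 states, and on the amendment route in SAP section 1 being used once the Period 4 dose is known.
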